# 4.5 Termination Criteria

Termination of the treatment does not mean the withdrawal from the study. Subjects must continue to complete the remaining study visits as required by the protocol. If the subject meets any of the following criteria, the treatment must be terminated:

- 1. Subjects withdraw their informed permission and request to be removed from the study.
- 2. Progressive disease is confirmed by investigator.
- 3. Pregnancy during the study.
- 4. the subjects cannot tolerate the toxicity after dose adjustment.
- 5. Other situations indicating the need to withdraw from the study.

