#### 5.2.4 Dose reduction

Dose adjustment is made at any time in each administration cycle. After the dose is reduced, it should not be brought back to the previous level. After the dose is adjusted to 250 mg q.d., continued dose adjustment is not allowed, including dose increase or decrease for any reason, but dose suspension is still allowed.

AE classification	NCI	Dose adjustment
		stop medication and continue to use the original dose when
Hematology AE	Grade 3	the AE $\leq$ Grade 2. If Grade 3 or above AEs occur again, the
		drug should be continued after a-dose reduction

Table 1 principle of dose adjustment of apatinib
--

	Grade 4	the drug is suspended, and the drug is continued after a-dose
		reduction and the AE recovered to $\leq$ Grade 2.
Non-hematological AE	Grade 3	The drug should be suspended until the AE $\leq$ Grade 1, and the
		drug should be continued with the original dose; if Grade 3 or
		above AEs occurs again, the drug should be continued after a-
		dose reduction.
	Grade 4	the drug is suspended, and the drug is continued after a-dose
		reduction and the AE recovered to $\leq$ Grade 1.

Note: the above evaluation is carried out according to NCI-CTCAE4.0

For subjects with gastrointestinal perforation, wound dehiscence, fistula, severe bleeding, nephrotic syndrome or hypertensive crisis, administration should be stopped permanently. Subjects with moderate to severe proteinuria or severe hypertension who need further diagnosis should stop using the drug temporarily.

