#### 6.2.2.2 Clinical stages of hypertension and routine treatment

- Prehypertension: (120-139/80-89 mmHg, or systolic blood pressure 120-139 mmHg): there is no indication of using antihypertensive drugs, only blood pressure is monitored
- Grade 1 hypertension: (140-159/90-99 mmHg, or systolic blood pressure is 140-159 mmHg): use drugs to reduce blood pressure and monitor blood pressure at the same time; most of them use thiazide diuretics, but also consider using ARB, ACEI, β-receptor blockers and calcium channel blockers; continue to take apatinib, and two anti-hypertensive drugs can be considered if the blood pressure is not ideal.
- ➤ Grade 2 hypertension: (160-179/100-109 mmHg, or systolic blood pressure ≥ 160-179 mmHg): combined use of two drugs (usually thiazide diuretics and ARB or ACEI or β-receptor blockers or calcium channel blockers); monitor blood pressure.
- Grade 3 hypertension: (≥180/110 mmHg, or systolic blood pressure≥180 mmHg): combined use of two drugs (usually thiazide diuretics and ARB or ACEI or β-receptor blockers or calcium channel blockers); closely monitor blood pressure; assess other risk factors (such as target organ damage, diabetes and other clinical symptoms), and take corresponding measures
- Hypertension crisis: refers to a serious clinical state in which blood pressure is excessively elevated and diastolic blood pressure exceeds 16.0-17.3 kPa (120-130 mmHg). At present, there is no unified classification at home and abroad. Recently, it can be divided into two types from the perspective of clinical treatment: (1) Hypertension emergencies: diastolic blood pressure>16.0 kPa (120 mmHg), accompanied by acute or progressive target organ damage, such as cerebral infarction, intracranial or subarachnoid hemorrhage, hypertensive

encephalopathy, and so on. Rapidly progressive hypertension based on chronic essential hypertension is the most common (about 40%~50%). (2) Hypertension urgencies: diastolic blood pressure>16.0 kPa (120 mmHg) without or with only slight organ damage; sodium nitroprusside or nifedipine is used to reduce blood pressure rapidly; diazepam and phenobarbital are used to stop convulsion; furosemide and mannitol are used to reduce intracranial pressure.

Note: in case of hypertension crisis, the use of apatinib should be stopped immediately and the patient should be withdrawn from the clinical trial.

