#### 6.2.4 Suggestions for proteinuria treatment

The subjects with two consecutive urinary protein (++) need 24-hour urinary protein quantification.

UPC < 3g	continue the treatment at the same dose, and monitor according to clinical indications
UPC $\geq$ 3g	Step 1: obtain 24-hour urine protein
	Step 2: if 24-hour urine protein < 3g, the treatment can be continued at the same dose
	If 24-hour urinary protein $\geq$ 3g, discontinue treatment until UPC

returns to < 3g, start treatment again at a lower dose, and monitor
UPC in the following whole treatment stage. If UPC $\ge$ 3g, 24-hour
urine protein is obtained.
Step 3: if 24-hour urine protein $\geq$ 3g after repeated reduction, terminate the trial, and follow up according to the protocol

Note: in case of nephrotic syndrome, the use of apatinib should be stopped immediately and the patient should be withdrawn from the clinical trial.

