# 7.5 Visit during follow-up

Subjects with early withdrawal, intolerable AEs, progressive disease in the randomization phase or progressive disease in the extension phase can enter the survival follow-up period.

- If the subjects have been evaluated within 4 weeks before the survival follow-up period, the survival follow-up and imaging efficacy evaluation should be conducted once every 2 months until imaging progression or other anti-tumor treatment is started.
- If the subjects have not been evaluated within 4 weeks before the survival follow-up period, a follow-up and evaluation of therapeutic efficacy (imaging examination, detection of serum Tg and TgAb levels, and thyroid function test (including FT3, FT4, TSH, RT3 [RT3 can be selected as needed]) and then the survival follow-up and imaging efficacy are conducted once every 2 months until imaging progression or other anti-tumor treatment is started.

During the follow-up period, the time of death or loss of follow-up and other anti-tumor treatment is recorded.

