#### 9.3.1 Events that should be dealt with as SAEs

In principle, pregnancy and lactation cannot be included. If pregnancy occurs during the trial, the patient should withdraw from the trial immediately and be followed up closely. Even if the mother and child are completely normal without any AEs, the situation should be recorded. Even if the pregnancy does not belong to SAEs, the SAEs report form should be used for reporting.

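### Sections 6.2.2.2, 6.2.4 and 9.3.1 take patients out of the trial after events for which 4.5 and 5.2.4 only stop treatment, so tumour assessment could end before progression

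*Protocol*

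**What the plan says.** Section 4.5 (Termination Criteria) opens with a general rule: "Termination of the treatment does not mean the withdrawal from the study". It continues: "Subjects must continue to complete the remaining study visits as required by the protocol". The list of reasons to end treatment that follows includes "Pregnancy during the study".

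Section 5.2.4 (Dose reduction) names several severe toxicities, among them "nephrotic syndrome or hypertensive crisis, administration should be stopped permanently". It says nothing about leaving the trial.

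Three other sections go further:

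- 6.2.2.2, closing note: "in case of hypertension crisis, the use of apatinib should be stopped immediately and the patient should be withdrawn from the clinical trial".
- 6.2.4, closing note: "in case of nephrotic syndrome, the use of apatinib should be stopped immediately and the patient should be withdrawn from the clinical trial".
- 9.3.1, on pregnancy: "the patient should withdraw from the trial immediately and be followed up closely".

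Two sections deal with what happens afterwards. Section 3.1 follows survival status every two months until death or loss to follow-up. Section 7.5 says that subjects with early withdrawal or intolerable adverse events, as well as those with progression, "can enter the survival follow-up period". For those who enter, survival follow-up and imaging take place every two months until imaging progression or other anti-tumour treatment.

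**The concern.** For the same three events the protocol gives two answers to the question of whether the patient stays in the study. PFS by RECIST 1.1 is the primary endpoint. Section 10.2.1 analyses it by Kaplan-Meier, log-rank test and Cox model, all of which take censoring to be unrelated to the risk of progression. A patient whose scans stop because of a severe toxicity is censored for a reason that may be related to that risk. If the toxicity is commoner in one arm, so is the censoring.

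The protocol's own RECIST attachment points the other way. Its section 4.4.4 asks for every effort to document objective progression after treatment has stopped. Its section 4.5 asks that assessment in randomised trials follow a calendar, unaffected by events that could make its timing differ between arms.

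**Working it through.** **The text, side by side**

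| Event | Treatment-stop rule | Instruction on the trial | Follow-up named at that place |
|---|---|---|---|
| Hypertensive crisis | 5.2.4: permanent stop | 6.2.2.2: withdrawn | None |
| Nephrotic syndrome | 5.2.4: permanent stop | 6.2.4: withdrawn | None in the note |
| Pregnancy | 4.5: treatment ends | 9.3.1: withdraw | Close follow-up, content not stated |

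The notes in 6.2.2.2 and 6.2.4 give stopping the drug and withdrawal from the trial as two separate acts, so the second is hard to read as another name for the first. Step 3 of the proteinuria table in 6.2.4 does add follow-up according to the protocol, whereas the nephrotic-syndrome note below it does not. The follow-up in 9.3.1 stands in the safety section and mentions neither tumour assessment nor survival. Section 4.5 says *must* about the remaining visits; 7.5 says *can*.

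**The plan's figures (3.3, 10.3)**

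Inputs: median PFS 5.8 and 12 months, 24 months of accrual, 12 months of follow-up, two-sided 0.05, 90% power, 50 per arm, 15% drop-out.

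- HR = 5.8/12 = 0.483, |ln HR| = 0.727.
- Events needed: 80 (Schoenfeld), 87 (Freedman). The stated 37 + 46 = 83 lies between them.
- Schoenfeld power at 83 events: Φ(√83 × 0.727/2 − 1.960) = Φ(1.352) = 91.2%. Freedman gives 88.7%.
- Event probability on apatinib, exponential PFS with uniform accrual and λ = ln 2/12: 1 − (e^(−12λ) − e^(−36λ))/(24λ) = 1 − (0.500 − 0.125)/1.386 = 0.729. For 50 patients this gives 36.5 events. The same formula gives 46.1 for control. Both match the plan.
- 50/0.85 = 58.8, so 59 per arm and 118 in total.

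**What a loss would do to power**

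The documents give no rate of hypertensive crisis or nephrotic syndrome, so the rates below are assumptions. Each lost apatinib patient is taken to leave before any event and never to be followed again. Events = 83 − (rate × 59 × 0.729).

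| Assumed share of 59 | Patients | Events left | Power (Schoenfeld) |
|---|---|---|---|
| 1% | 0.6 | 82.6 | 91.0% |
| 2% | 1.2 | 82.1 | 90.9% |
| 5% | 3.0 | 80.8 | 90.5% |
| 10% | 5.9 | 78.7 | 89.7% |

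This is a pessimistic bound. It takes patients from 59 but subtracts from the 83 events expected of 50 per arm; 59 fully followed apatinib patients would give 59 × 0.729 = 43.0 events, not 37. The 59 − 50 = 9 extra patients per arm are there for drop-out. Section 10.4 also ties the final analysis to about 83 events, so lost patients would mainly delay it.

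These figures concern power only. Neither the size nor the direction of any bias can be derived from the documents.

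**The case against.** The strongest reply is that the protocol provides for follow-up after withdrawal. Section 7.5 names early withdrawal and intolerable adverse events and sets two-monthly imaging. Its permissive verb also covers patients with progression, so it does not single out the withdrawn. Section 3.1 follows survival without condition. Section 9.3.1 asks for close follow-up in pregnancy. The notes to the schedule in 7.1 ask for a closing assessment on early withdrawal if none was done in the previous four weeks. The protocol also uses its terms loosely: 4.5 lists situations that call for withdrawal from the study among its reasons to end treatment, under a rule that visits continue.

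Much of this stands. A reader might infer that the protocol orders PFS and OS follow-up to end for these patients. It does not: loss of follow-up is a risk that the wording creates, and for OS section 3.1 makes it smaller still. What the reply does not remove is the conflict itself. A single closing scan is not continued assessment, and a site can read *can* together with withdrawal from the trial as permission to stop imaging.

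A reader might also infer that the losses would fall almost wholly on apatinib. The only figure is 30% Grade 3 hypertension among ten single-arm patients at 750 mg (section 1.3). That is neither hypertensive crisis nor the dose of this trial, and nephrotic syndrome is not mentioned there. Section 6.2 handles hypertension and proteinuria as common adverse events, which makes an excess on apatinib plausible but does not measure it. Nothing links pregnancy to an arm. For OS, placebo patients may receive apatinib after progression (3.1, 7.4) and then face the same toxicities.

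**Conclusion.** The contradiction is real for all three events and rests on the text alone. Its consequence is conditional: if a site follows the notes literally and treats 7.5 as optional, tumour assessment can stop before progression, and the resulting censoring may be informative for PFS. An excess on apatinib is a plausible inference for hypertensive crisis and nephrotic syndrome only. The effect on power is small, at most 1.5 percentage points (91.2% to 89.7%) under an assumed 10% loss with no event before it and no follow-up after it. The point is therefore possible bias and uneven conduct between sites, not a shortage of events. It merits correction because it touches the primary endpoint and is cheap to put right.

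**What to change.** Reconcile 4.5, 5.2.4, 6.2.2.2, 6.2.4, 7.5 and 9.3.1 so that stopping study drug is stated separately from ending tumour and survival follow-up. Follow-up should continue, as 4.5 already requires, unless the patient withdraws consent. The permissive wording on entering follow-up in 7.5 should be brought into agreement with the obligation in 4.5.

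The rules on when treatment stops are left as they stand, and no clinical rule is proposed, including on imaging in pregnancy; how the passages are reconciled in that respect is for the sponsor. The cost is a protocol wording change and, for a few patients, visits that 4.5 already requires. The sample size does not change.

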# 6.2.3 Management of gastrointestinal bleeding

Gastrointestinal bleeding, including fecal occult blood (++), hematemesis or bloody stool, should be treated actively. Subjects with upper gastrointestinal bleeding should be fasting, and given antacids, gastric mucosal protection drugs, hemostatics (hemostatic acid, reptilase, etc.), if necessary, octreotide can be used; Subjects with lower gastrointestinal bleeding should be given hemostasis, blood transfusion and support treatment; if bleeding cannot be controlled, surgical assistance is needed.

#### 6.2.4 Suggestions for proteinuria treatment

The subjects with two consecutive urinary protein (++) need 24-hour urinary protein quantification.

UPC < 3g	continue the treatment at the same dose, and monitor according to clinical indications
UPC $\geq$ 3g	Step 1: obtain 24-hour urine protein
	Step 2: if 24-hour urine protein < 3g, the treatment can be continued at the same dose
	If 24-hour urinary protein $\geq$ 3g, discontinue treatment until UPC

returns to < 3g, start treatment again at a lower dose, and monitor
UPC in the following whole treatment stage. If UPC $\ge$ 3g, 24-hour
urine protein is obtained.
Step 3: if 24-hour urine protein $\geq$ 3g after repeated reduction, terminate the trial, and follow up according to the protocol

Note: in case of nephrotic syndrome, the use of apatinib should be stopped immediately and the patient should be withdrawn from the clinical trial.

## 6.2.5 Thyroid function

During the whole treatment period, thyroid function of all subjects is closely monitored. TSH should be controlled at <0.1uIU/mL. If it exceeds the range, corresponding treatment should be given.

# 7 Study Procedures

# 7.1 Study Schedule

	Visit during the screening		Visit during the treatment						Visit during	Vist during follow- up	
Item			1 st cycle			2 nd cycle		3 rd cycle and after	extension phase	every 2 months	
	(-14~0 d)	(-7~0 d)	7d	14d	21d	28d	42d	56d			
Visit	v	1	V2	V3	V4	V5	V6	V7	V8-Vn	V'1-V'n	
Informed consent	x										
Past treatment history		X									
Vital signs a		x		x		X	x	x	#	&	
Physical examination		x				x		x	#	&	
Blood pressure b		x	X	x	x	x	x	x	#	&	
Myocardial enzyme spectrum and color Doppler ultrasound e	x			x		x		x	#	&	
Coagulation function		x				x		x	#	&	
Electrocardiogram	x			x		x		x	#	&	
ECOG PS score		x				x		x	#	&	
Blood routine		x	X	X	X	X	x	x	#	&	

Urinalysis		X		x		X		x	#	&	
-											
Defecation routine		X		x		x		x	#	&	
Liver and kidney		X		x		x		x	#	&	
function, electrolytes		Χ		А		Χ		А	#	a	
Imaging examination											
(X-ray/CT/MRI/B-	X					x		X	&@	&@	
ultrasound) d											
Serum Tg and TgAb		X		X		x	X	X	&@	&@	
Thyroid function e		X		x		x	Х	X	&@	&@	
Life quality score		X				X		X	#	&	
Hamilton Depression		X									
Scale score		A									
Pregnancy test (blood)		X									
Collection of whole											
blood and plasma		x f							@	@	
samples											
Tissue specimen		X									
collection		A									
AE			X	x	X	x	X	X	#	#	
Concomitant medication			x	x	x	x	X	x	#	#	
Death time											X

|--|

Note: (1) &: once every 2 cycles (the last day); (2) #: once every cycle (last day) and once every 2 cycles (last day) after 6 cycles of medication; (3) @: when the progressive disease or withdraw from the study in advance, if there is no such examination result within 4 weeks before the end of the trial, it needs to be collected within 7 days after the end of the study; (4) a: The subjects can increase the frequency of self-examination of vital signs according to their own conditions and fill in the relevant abnormal conditions in the research diary card. b: blood pressure monitoring: blood pressure monitoring is completed by the subjects themselves, at least three days a week in the first two cycles after medication, and once a week in the later cycles. Once abnormal, the blood pressure should be monitored to the normal level every day and recorded in the patient's diary card; in addition, the blood pressure is measured again by the researcher at each follow-up. During the blood pressure measurement, smoking and coffee drinking are prohibited within 30 minutes before the measurement, and at least 10 minutes of quiet rest are taken. During the measurement, the sitting position is taken, the elbow is placed at the same level as the heart, and each blood pressure measurement is taken on the same side. c. Myocardial enzyme spectrum and color Doppler ultrasound: supplement this examination when ECG is abnormal and has clinical significance; d: if chest, abdomen or pelvis imaging examination is negative at screening, X-ray or B-ultrasound should be used for examination during the study period; if X-ray or B-ultrasound shows positive results, CT or MRI scan should be used to confirm; e: the examination items include FT3, FT4, TSH, RT3 [RT3 can be selected as needed]; f: collect within 3 days after the first medication. (5) Tumor samples (tissue and blood) are collected when subjects include in this study. If a tumor sample is not collected, the reason should be record. (6) During the first two cycles of treatment, all examinations and life quality scores are performed within  $\pm 3$  days of the corresponding date, and after two cycles, all examinations and life quality scores are performed within  $\pm 7$  days of the corresponding date.

